1.0 Objectives

Table 1: Objectives, Endpoints, and Justifications					
Objectives	Endpoints	Justification			
Primary	Primary	Primary			
Evaluate the effectiveness of	ED-15 score	ED-15 is an evidenced-based			
oral naltrexone tablets in		metric of eating disorder			
pediatric and adolescent eating		symptom severity and			
disorders, particularly anorexia		frequency.			
nervosa and bulimia nervosa, as					
compared to placebo.					
Secondary	Secondary	Secondary			
Evaluate the effect of oral	Improvement on Eating	Naltrexone has some effect on			
naltrexone on desire to self-	Disorder Examination	desire to self-harm, and this can			
harm and impulsivity in patients	Questionnaire (EDE-Q), Patient	be examined in eating disorder			
with eating disorders	Health Questionnaire-9 (PHQ-	patients. EDE-Q, GAD-7, PHQ-			
	9), Generalized Anxiety	and BIS/BAS measure other			
	Disorder-7 (GAD-7), Alexian	features of eating disorder			
	Brothers Urge to Self-Injury				
	Scale (ABUSI), and Behavioral				
	Inhibition System/Behavioral				
	Activation System score				
	(BIS/BAS), need for escalation of				
	level of care, desire to restart				
	study article, and rate of weight				
	restoration.				
Tertiary/Exploratory	Tertiary/Exploratory	Tertiary/Exploratory			
none					

1.1 Study Objectives

Describe the purpose, specific aims or objectives. State the hypotheses to be tested.

The objective of this study is to evaluate the effectiveness of oral naltrexone tablets in pediatric and adolescent eating disorders, in particular anorexia nervosa and bulimia nervosa, as compared to placebo. The hypothesis of this study is that patients receiving oral naltrexone will demonstrate greater improvement in their score on the ED-15, an evidence-based metric of eating disorder symptom severity and frequency¹, than those receiving placebo, representing more complete recovery from eating disorder

1.2 Primary Study Endpoints

State the primary endpoints to be measured in the study.

Clinical trials typically have a primary objective or endpoint. Additional objectives and endpoints are secondary. The endpoints (or outcomes), determined for each study subject, are the quantitative measurements required by the objectives. Measuring the selected endpoints is the goal of a trial (examples: response rate and survival).

The primary outcome will be clinically and statistically significant reduction in ED-15 score in those receiving medication vs placebo.

1.3 Secondary Study Endpoints

State the secondary endpoints to be measured in the study.

Secondary outcomes will include improvement in scores on Eating Disorder Examination Questionnaire (EDE-Q)², the Patient Health Questionnaire-9 scale (PHQ-9,, a measure of depression)³ the Generalized Anxiety Disorder-7 scale(GAD-7, an inventory of anxiety)⁴, Alexian Brothers Urge to Self-Injure Scale (ABUSI; an inventory measuring the desire to self-harm)⁵, and Behavioral Inhibition System/Behavioral Activation System score (BIS/BAS; an impulsivity inventory)⁶; need for escalation of level of care (such as requirement for early termination of partial hospitalization program to attend inpatient or residential eating disorder care or hospitalization for medical stabilization); and rate of weight restoration.

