3.2 Exclusion Criteria

Create a numbered list of the exclusion criteria that define who will be excluded in your study.

- Diagnosis of intellectual disability
- History of known genetic or neurologic disease
- Need for treatment with opioid painkillers
- Weight <25kg
- Inability to swallow pills
- Lack of proficiency in written or spoken English
- Urine drug screen positive for opioids at enrollment
- Positive serum pregnancy test at enrollment
- Lactation
- Elevation of three times the upper limit of normal for age in either alanine aminotransferase (ALT) or asparagine aminotransferase (AST).
- High risk of suicide at enrollment on Columbia Suicide Severity Rating Scale (C-SSRS, for participants age 18)²⁰ or Ask Suicide Screening Questions (ASQ, participants age 13 to 17)²¹
- Current Naltrexone use

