8.0 Subject Numbers and Statistical Plan

8.1 Number of Subjects

Indicate the maximum number of subjects to be accrued/enrolled. Distinguish between the number of subjects who are expected to be enrolled and screened, and the number of subjects needed to complete the research procedures if applicable (i.e., numbers of subjects excluding screen failures.)

Because this is a pilot study, we have decided *a priori* to enroll 30 participants in each arm of treatment for a total of sixty subjects. In 2019, approximately 150 patients meeting criteria for potential inclusion (between ages of 12-18, needing PHP level of care in the eating disorder clinic, no diagnosis of gender dysphoria or intellectual disability, with diagnoses of anorexia nervosa, or bulimia nervosa) were seen for initial evaluation in the eating disorder clinic. Therefore we hope to be able to enroll sixty participants over the course of 12 to 18 months.

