8.2 Sample size determination

If applicable, provide a justification of the sample size outlined in section 8.1 to include reflections on, or calculations of, the power of the study.

This is a pilot study, and enrollment size was determined *a priori* to allow for completion of enrollment within 18 months.

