8.3 Statistical methods

Describe the statistical methods (or non-statistical methods of analysis) that will be employed.

For analysis, data will be analyzed for differences between participants receiving naltrexone and participants receiving placebo. The data will be analyzed for demography differences between the two groups at baseline, and outcomes will be compared at three and six weeks; as well as at 6 months. Outcomes to be compared are stated in section 1.1 and 1.2. Within each group, these outcomes will also be compared across time. Statistically significant differences between each group at each endpoint will be noted and reported.

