10.0 Risks

List the reasonably foreseeable risks, discomforts, hazards, or inconveniences to the subjects related the subjects' participation in the research. Include as may be useful for the IRB's consideration, a description of the probability, magnitude, duration and reversibility of the risks. Consider all types of risk including physical, psychological, social, legal, and economic risks. Note: Loss of confidentiality is a potential risk when conducting human subject research.

- If applicable, indicate which procedures may have risks to the subjects that are currently unforeseeable.
- If applicable, indicate which procedures may have risks to an embryo or fetus should the subject be or become pregnant.
- If applicable, describe risks to others who are not subjects.

Risks associated with taking oral naltrexone:

- elevated transaminases
- depression and mood changes
- abdominal pain
- nausea
- headache

Additional clinical risks that could be associated with taking Oral Naltrexone:

- Some pediatric autism literature describes low appetite or occasionally worsening of self-injurious behavior while on naltrexone^{8,11,22,22–25,27}. There can also be worsening depression according to the FDA label⁷. These adverse effects are occasionally seen with PHP for eating disorder itself, and therefore we monitor for them frequently as a part of the standard of care. Should the subject or the subject's parent wish to withdraw from the study due to these effects, they are free to do so. If these adverse effects are felt to be related more to the natural history of eating disorder and not to study intervention; or the severity is minor to moderate; the subject may continue to participate in the study if desired. If the effect is severe the subject will be withdrawn.
- Oral naltrexone is a pregnancy category C medication⁷, where there are animal studies that may indicate
 harm to the fetus but no specific human studies on this topic. For this reason, we will test for pregnancy
 in allbirth-assigned females at enrollment using a serum pregnancy screen, and every three weeks
 throughout the study using a urine pregnancy screen. The majority of patients enrolled in child PHP
 have not yet had coitarche, though in adult PHP a history of sexual activity is more common.

Other risks of participation include:

- Loss of confidentiality
- Risk of randomization
- Risk of incidental findings
 Anxiety from completing questionnaires

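### ABUSI, the only measure of desire to self-harm, is to be compared between arms without baseline adjustment or a count of new urges, in participants not selected for having urges

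*Combined protocol and SAP*

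**What the plan says.** Table 1 (section 1.0) sets one secondary objective: the effect of naltrexone on the wish to self-harm and on impulsivity in patients with eating disorders. Section 1.3 opens with "Secondary outcomes will include improvement in scores on" and lists several scales. Only one is described as measuring that wish, the "Alexian Brothers Urge to Self-Injure Scale (ABUSI; an inventory measuring the desire to self-harm"). No change definition, time point or threshold is attached to it.

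The other relevant parts of the plan are these:

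- **Eligibility (3.1).** The diagnosis must involve bingeing or purging. No history of self-harm and no minimum ABUSI score is required. Section 3.2 excludes "High risk of suicide at enrollment on Columbia Suicide Severity Rating Scale" (or on the equivalent screen for minors).
- **Randomization (7.3.3).** Stratified by age and diagnosis, not by self-harm urges.
- **Schedule (7.1, 7.2).** ABUSI is taken at enrollment, weeks 1, 3 and 6, week 8 or 9, and six months. Study medication ends at week 6.
- **Analysis (8.3).** Naltrexone is compared with placebo, and "outcomes will be compared at three and six weeks; as well as at 6 months". No test, model, baseline adjustment, analysis set or lead time point is named. The outcomes are taken from sections 1.1 and 1.2, so section 1.3, where ABUSI is listed, is not cited.
- **Risk (10.0).** The pediatric autism literature is said to describe "occasionally worsening of self-injurious behavior while on naltrexone".
- **Safety data (9.2, 9.7).** New self-injurious behavior is sought by chart review and survey results are monitored, but no statistical tests of safety data are planned.

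**The concern.** A scale with a minimum cannot register improvement in someone who already scores the minimum. Such a participant can only stay put or get worse. Because enrollment ignores self-harm urges, the trial may include a sizeable group of this kind, and a between-arm mean over everyone would then contain two distinct things.

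The first is dilution. A real reduction in urges among those who have them is averaged with zeros. Without baseline adjustment, the large enrollment difference between people with and without urges also stays in the error term.

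The second is masking. If naltrexone provokes urges in some people who had none, that rise pulls against the benefit in others and is not visible as a separate result.

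At stake is the self-harm half of the only secondary objective. A real effect in those with urges could read as a small, inconclusive difference, while a safety signal that section 10.0 anticipates would not be reported by arm.

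**Working it through.** **Plan's own figure.** Section 8.1 will "enroll 30 participants in each arm of treatment for a total of sixty subjects". Section 8.2 says the number was chosen "to allow for completion of enrollment within 18 months". No effect size, SD, alpha or power is given, so there is no power calculation to reproduce. Everything below except 30 per arm is an assumption.

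**Inputs assumed.** Two-sided 5%. A share *f* has urges at enrollment; naltrexone lowers their score by *d* = 0.8 SD (SD of their change = 1). The rest sit at the minimum with no drug effect and change SD *s0* between 0 and 1. Placebo participants with urges have mean change 0.

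**Dilution.**
- Difference over everyone = *f* × *d*.
- Variance on naltrexone = *f* + (1−*f*)*s0*² + *f*(1−*f*)*d*²; on placebo = *f* + (1−*f*)*s0*². SD is the root of their average.
- Power = Φ(*f d*/SD × √(30/2) − 1.96).

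For *f* = 0.5, *s0* = 0: difference 0.40; variances 0.66 and 0.50; SD = √0.58 = 0.76; power = Φ(0.40/0.76 × 3.87 − 1.96) = 53%. With *s0* = 1: SD = √1.08 = 1.04 and power 32%.

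| Share with urges | Difference, everyone (SD) | Power, everyone | Power, only those with urges (n per arm) |
|---|---|---|---|
| 100% | 0.80 | 87% | 87% (30) |
| 70% | 0.56 | 56–70% | 74% (21) |
| 50% | 0.40 | 32–53% | 59% (15) |
| 30% | 0.24 | 15–34% | 40% (9) |

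Ranges run from *s0* = 1 to *s0* = 0. Restricting to those with urges restores the 0.8 SD effect but shrinks the sample. When *s0* is 0 and *f* is 30% to 70%, the gain in power is only about 4 to 6 points.

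**Baseline adjustment.** A simulation with 30 per arm used these settings: those with urges average 2 SD above the minimum at enrollment, correlation 0.6 with week 6, the same 0.8 SD benefit, scores cut off at the minimum, and 5% background new urges in the rest. With half having urges and no added harm:
- plain week-6 comparison in everyone: about 26%;
- adjusted for enrollment ABUSI, everyone: about 65%;
- adjusted, only those above the minimum: about 70%.

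A change-score test lies between the first two. With 30% having urges, adjustment in everyone gives about 39%, against 45% in those with urges. Most of what can be recovered therefore comes from adjustment, not from restriction.

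**Masking.** Suppose an extra share *g* of those at the minimum worsens by *w* SD on naltrexone. The net difference is *f d* − (1−*f*)*g w*.
- *f* = 0.5: *g* = 0.1, *w* = 0.5 gives 0.40 − 0.025 = 0.375 (6% lost); *g* = 0.2, *w* = 1 gives 0.40 − 0.10 = 0.30 (25% lost).
- *f* = 0.3: the same two cases give 0.205 (15% lost) and 0.10 (58% lost).
- Full cancellation at *w* = 1 needs *g* = 0.40/0.50 = 80% for *f* = 0.5, or 0.24/0.70 = 34% for *f* = 0.3.

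The effect on power depends heavily on how high new urges score. With half having urges and new urges raised by 15 points on naltrexone, the adjusted all-participant analysis has about 57%, 41% or 20% power when new urges score about 0.5, 1 or 2 SD.

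**The case against.** The case for leaving the plan alone has real strength.

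- **The share at the minimum is unknown.** The documents give no ABUSI range or distribution. If few participants sit at the minimum, little is lost. This stands, and it is why no single size can be quoted.
- **The all-randomized comparison is a valid answer.** Table 1 asks about patients with eating disorders, and a net effect that includes harm answers that. This stands. A reader might infer that the main analysis should be confined to people with urges. The figures do not support that: the gain over adjustment in everyone is about 5 points at half with urges, and it would demote the randomized comparison for an unstratified subset of perhaps 9 to 15 per arm.
- **Harm is already monitored.** Chart review, survey results and weekly suicidality screening are planned (9.1 to 9.3). But section 9.5 reports only events judged due to participation, section 10.0 allows such effects to be put down to the eating disorder, and no by-arm count of new urges is planned. The objection weakens the point without removing it.
- **Section 10.0 concerns behavior, not urges, and worsening, not onset.** That harm could also fall among people who already have urges. So it would be wrong to infer that those with urges can show only benefit; they can worsen too, and no split by enrollment score separates benefit cleanly from harm.

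Two other inferences go too far. One is that new urges would cancel the benefit and produce a null result; under these assumptions that needs 34% to 80% of those at the minimum to worsen by a full SD, and section 10.0 says only that worsening occurs occasionally. The other is that the suicide-risk exclusion strips out high ABUSI scorers; it concerns a different construct, and the documents do not link the two.

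**Conclusion.** The point holds as a gap in how the ABUSI endpoint is to be analyzed. It does not show that the endpoint is unusable. Any participants at the minimum at enrollment dilute the mean difference in proportion to their share, and any excess of new urges among them on naltrexone would partly offset benefit elsewhere and go unreported as such. The masking argument presumes that means are compared. Section 8.3 does not say so; if improvement were analyzed as a proportion of improvers, new urges would simply count as no improvement.

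The size rests on assumptions. For 30% to 70% with urges and a 0.8 SD benefit, the all-participant difference is 0.24 to 0.56 SD. Masking removes about 6% to 25% of the diluted difference at half with urges, and 15% to 58% at 30%, over the values tried. That all 60 would be analyzed is the default reading only: section 8.3 names no analysis set, and section 3.3.2 uses data only up to withdrawal.

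The firmest conclusion is that adjusting for enrollment ABUSI recovers most of the avoidable loss (about 26% to 65% power in the half-with-urges illustration), and that a by-arm count of new urges shows what a pooled mean cannot.

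**What to change.** In section 8.3, which should also cite section 1.3:

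1. Define the ABUSI analysis as the week-6 (end of treatment) difference between arms in all randomized participants, adjusted for enrollment ABUSI.
2. Among participants at the scale minimum at enrollment, report by arm, as a harm outcome, the proportion with any urge at a later visit. The numbers will be small: with half at the minimum there are 15 per arm, so 5% against 20% would be 0.75 against 3 expected participants. This is a description, not a test.
3. Add a prespecified, baseline-adjusted analysis of participants above the minimum at enrollment, labelled exploratory, to support item 1 and not replace it.

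The cost is a few sentences and two short extra analyses. No new visits or data are needed, since ABUSI is already scheduled at enrollment and later visits. The drawback is that the subset estimate will be imprecise, at roughly 9 to 15 per arm if 30% to 50% have urges (0.3 × 30 and 0.5 × 30), and fewer after withdrawals. Settling the definitions before unblinding also rules out choosing the subset after seeing the results.

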2.0 Background

2.1 Scientific Background and Gaps

Describe the scientific background and gaps in current knowledge.

For clinical research studies being conducted at Penn State Health/Penn State College of Medicine, and for other non-PSH locations as applicable, describe the treatment/procedure that is considered standard of care (i.e., indicate how patients would be treated in non-investigational setting); and if applicable, indicate if the treatment, drug, or device is available to patient without taking part in the study.

Oral naltrexone (Revia) is a long-acting opioid antagonist with approval from the Food and Drug Administration (FDA) for treatment of alcohol use disorder and provision of opioid receptor blockade⁷. It has demonstrated some utility in treating harmful, self-stimulatory behaviors (self-injurious behavior, SIB) in patients with autism (such as head-banging, self-mutilation, etc)⁸. It is generally well-tolerated, with few side effects outside of limiting the effectiveness of opioid medication⁷. Oral naltrexone became a therapeutic agent in the context of autism with SIB related to the "opioid hypothesis" of autism, namely, that the stereotyped behaviors of autism resembled those of addiction^{9,10}. There are two proposed mechanisms of action for oral naltrexone in reducing self-harming behaviors: one, naltrexone disrupts serotonergic reward pathways that reinforce SIB¹¹; and two, those with SIB have chronically elevated endogenous opioid production, where SIB increases endogenous opioid activity directly¹⁰.

There is some evidence of the value of treatment with naltrexone in bulimia¹² and binge-eating disorder ^{13,14}, though intranasal naloxone, a related compound, has been shown to not be more efficacious than placebo in binge-eating disorder¹⁵. There is some evidence to suggest that naltrexone may be helpful in anorexia nervosa in adult patients¹⁶. A retrospective chart review of pediatric patients with bulimia did reveal subjective improvement in purging behaviors in patients taking oral naltrexone, however this study was retrospective, cross-sectional, unblinded, without a control group, and did not account for the effect of eating disorder therapy itself¹⁷.

There is relatively little data regarding use of pharmacologic agents in anorexia nervosa, in particular in pediatric patients^{14,18}. The objective of this study is to evaluate the effectiveness of oral naltrexone tablets in pediatric and adolescent eating disorders, in particular anorexia nervosa and bulimia nervosa, as compared to placebo.

2.2 Previous Data

Describe any relevant preliminary data.

The investigators for this specific study do not have any of their own preliminary data.

2.3 Study Rationale

Provide the scientific rationale for the research.

We hypothesize that oral naltrexone will provide additional treatment benefit for adolescents and young adults between age 13-25 who have compulsive behavior related to eating disorder, including bingeing, self-induced vomiting, compulsive exercise, or other inappropriate compensatory behaviors. We believe this because adult literature has demonstrated some efficacy of oral naltrexone in these areas, and pediatric autism literature has demonstrated safety in this age group.

3.0 Inclusion and Exclusion Criteria

Create a numbered list below in sections 3.1 and 3.2 of criteria subjects must meet to be eligible for study enrollment (e.g., age, gender, diagnosis, etc.).

Vulnerable Populations:

Indicate specifically whether you will include any of the following vulnerable populations in this research. You MAY NOT include members of these populations as subjects in your research unless you indicate this in your inclusion criteria because specific regulations apply to studies that involve vulnerable populations.

The checklists referenced below outline the determinations to be made by the IRB when reviewing research involving these populations. Review the checklists as these will help to inform your responses throughout the remainder of the protocol.

- Children –Review "HRP-416- Checklist Children"
- Pregnant Women Review "HRP-412- Checklist Pregnant Women"
- Cognitively Impaired Adults- Review "HRP-417- Checklist Cognitively Impaired Adults"
- **Prisoners-** Review "HRP-415- Checklist Prisoners"
- Neonates of uncertain viability or non-viable neonates- Review "HRP-413- Checklist Non-Viable Neonates" or "HRP-414- Checklist - Neonates of Uncertain Viability"

[Do not type here]

3.1 Inclusion Criteria

Create a numbered list of the inclusion criteria that define who will be included in your final study sample (e.g., age, gender, condition, etc.)

- Ages 13-25 (inclusive)
- Any sex
- Diagnoses of anorexia nervosa binge-purge subtype, bulimia nervosa, purging disorder, or atypical anorexia nervosa with bingeing or purging behaviors according to the Diagnostic and Statistical Manual version 5 diagnostic criteria
- Electing to participate in child or adult partial hospitalization program for eating disorder treatment at MSHMC
- The diagnostic criteria for anorexia nervosa, binge-purge subtype, are:
 - A. Restriction of energy intake relative to requirements, leading to a significantly low body weight in the context of age, sex, developmental trajectory, and physical health.

- Significantly low weight is defined as a weight that is less than minimally normal or, for children and adolescents, less than minimally expected.
- B. Intense fear of gaining weight or of becoming fat, or persistent behavior that interferes with weight gain, even though at a significantly low weight.
- C. Disturbance in the way in which one's body weight or shape is experienced, undue influence of body weight or shape on self-evaluation, or persistent lack of recognition of the seriousness of the current low body weight
- D. During the last three months the individual has engaged in recurrent episodes of binge eating or purging behaviour (i.e. self-induced vomiting, or the misuse of laxatives, diuretics, or enemas).¹⁹
- E. A diagnosis of atypical anorexia nervosa can be made when the body weight is normal or high If these patients engage in bingeing or purging behaviors as defined in anorexia nervosa, binge-purge subtype, they are eligible for inclusion in this study
- The diagnostic criteria for bulimia nervosa are:
 - A. Recurrent episodes of binge eating. An episode of binge eating is characterized by
 - B. both:
 - i. Eating in a discrete period of time (e.g. within any 2 hour period), an amount of food that is definitely larger than what most individuals would eat in a similar period of time under similar circumstances;
 - ii. A sense of lack of control over eating during the episodes (e.g. a feeling that one cannot stop eating or control what or how much one is eating.
 - C. Recurrent inappropriate compensatory behaviors to prevent weight gain, such as self-induced vomiting; misuse of laxatives, diuretics, or other medications; fasting; or excessive exercise.
 - D. The binge eating and inappropriate compensatory behaviors both occur, on average, at least once a week for 3 months.
 - E. Self-evaluation is unduly influenced by body shape and weight.
 - F. The disturbance does not occur exclusively during episodes of anorexia nervosa.
- The diagnostic criteria for purging disorder are: recurrent purging behavior to influence weight or shape (e.g. self-induced vomiting; misuse of laxatives, diuretics, or other medications) in the absence of binge eating.

